#### **Reporting to UCSF IRB**

The PI must report events meeting the UCSF IRB definition of “Unanticipated Problem” (UP) within 10 business days of his/her awareness of the event.

### **Expedited Reporting to the FDA**

If the study is being conducted under an IND, the Sponsor-Investigator is responsible for determining whether or not the suspected adverse reaction meets the criteria for expedited reporting in accordance with Federal Regulations (21 CFR §312.32).

The Investigator must report via an IND safety report any suspected adverse reaction that is SUSAR (Suspected unexpected serious adverse reaction). The Sponsor-Investigator needs to ensure that the event meets all three definitions:

- Suspected adverse reaction (as defined in 7.2.2.1)
- Unexpected (as defined in 7.2.2.2)
- Serious (as defined in 7.3.3.3)

If the AE does not meet all three of the definitions, it should not be submitted as an expedited IND safety report.

The timeline for submitting an IND safety report to FDA is no later than **15 calendar days** after the Investigator determines that the suspected adverse reaction qualifies for reporting (21 CFR 312.32(c)(1)).

Any unexpected fatal or life-threatening suspected adverse reaction will be reported to FDA no later than **7 calendar days** after the Investigator’s initial receipt of the information (21 CFR 312.32(c)(2)).

Any relevant additional information that pertains to a previously submitted IND safety report will be submitted to FDA as a Follow-up IND Safety Report without delay, as soon as the information is available (21 CFR 312.32(d)(2)).

### **Reporting to Pharmaceutical Companies providing Study Drug**

AstraZeneca/MedImmune retains the right to request additional information for any patient with ongoing AE(s)/SAE(s) at the end of the study, if judged necessary.

All SAEs will be reported, whether or not considered causally related to the IP or to the study procedure(s). The investigator and/or Sponsor are responsible for informing the Ethics Committee and/or the Regulatory Authority of the SAE as per local requirements.

The following variables will be collected for AEs, for reporting to AstraZeneca

- AE (verbatim)
- The date when the AE started and stopped
- CTCAE Grade
- Whether the AE is serious or not
- Investigator causality rating against the IP (yes or no), comparator/combination drug (yes/no)
- Action taken with regard to IP/comparator/combination agent
- AE caused participant’s withdrawal from study (yes or no)
- Outcome

In addition, the following variables will be collected for SAEs:

- Date AE met criteria for SAE
- Date Investigator became aware of SAE
- AE is serious due to
- Date of hospitalization
- Date of discharge
- Probable cause of death
- Date of death
- Autopsy performed
- Causality assessment in relation to Study procedure(s)
- Causality assessment in relation to Other medication
- Causality assessment in relation to Additional Study Drugs
- Description of AE

The investigator and/or sponsor must inform the FDA, via a MedWatch form, of any serious or unexpected AEs that occur and will concurrently forward all such reports to AstraZeneca. A copy of the MedWatch report must be emailed to AstraZeneca at the time the event is reported to the FDA. It is the responsibility of the sponsor to compile all necessary information and ensure that the FDA receives a report according to the FDA reporting requirement timelines and to ensure that these reports are also submitted to AstraZeneca at the same time.

If a non-serious AE becomes serious, this and other relevant follow-up information must also be provided to AstraZeneca and the FDA.

SAEs that do not require expedited reporting to the FDA still need to be reported to AstraZeneca preferably using the Medical Dictionary for Regulatory Activities (MedDRA) coding language for SAEs. This information should be reported on a monthly basis and under no circumstance less frequently than quarterly.

\*A **cover page** should accompany the **MedWatch** form indicating the following:

- Investigator Sponsored Study (ISS)
- The investigator IND number assigned by the FDA
- The investigator's name and address
- The trial name/title and AstraZeneca ISS reference number

\*Investigative site must also indicate, either in the SAE report or the cover page, the **causality** of events **in relation to all study medications** and if the SAE is **related to PD**, as determined by the PI.

**\*Send SAE report and accompanying cover page by way of email to AstraZeneca's designated mailbox:** [REDACTED]. If a non-serious AE becomes serious, this and other relevant follow-up information must also be provided to AstraZeneca and the FDA.

All SAEs have to be reported to AstraZeneca, whether or not considered causally related to the IP. All SAEs will be documented. The investigator is responsible for informing the IRB and/or the Regulatory Authority of the SAE as per local requirements.

Non-serious AEs and SAEs will be collected from the time consent is given, throughout the treatment period and up to and including the *30 day follow-up* period. After withdrawal from treatment, participants must be followed-up for all existing and new AEs for *30 calendar days after the last dose of trial drug and/or until event resolution*. All new AEs occurring during that period must be recorded (if SAEs, then they must be reported to the FDA and AstraZeneca). All

study-related toxicities/SAEs must be followed until resolution, unless in the Investigator's opinion, the condition is unlikely to resolve due to the patient's underlying disease.

## 8 Statistical Considerations and Evaluation of Results

**Table 8.1 Study Endpoints**

	Objective	Endpoint
Primary	To evaluate the efficacy of osimertinib as neoadjuvant therapy in patients with surgically resectable EGFR-mutant NSCLC.	To determine the MPR rate, defined as $\leq 10\%$ viable tumor present histologically in the resected tumor specimen.
Secondary	To evaluate the safety and tolerability of osimertinib given as neoadjuvant therapy in early stage EGFR-mutant NSCLC patients. To evaluate secondary measures of clinical efficacy in early stage EGFR-mutant NSCLC patients treated with osimertinib induction therapy.	
 
• Radiographic decrease in maximum tumor diameter
 
• 5-year DFS
 
• 5-year OS
 
• DpR
 
• Complete pathological response rate
 
• Treatment-emergent AEs, laboratory abnormalities and ECG abnormalities as determined by NCI-CTC version 4.0 by investigator.
 
• Rate of inability to undergo surgical resection due to treatment-related AE.
 
• Rate of surgical complications occurring prior to end of treatment visit.
 

Exploratory	To evaluate long-term measures of efficacy in patients treated with osimertinib neoadjuvant therapy. To explore tissue and cell-free biomarkers that may be predictive of response or primary resistance to osimertinib neoadjuvant therapy.	
 
• Evaluate rates of adverse pathologic features on resection specimens.
 
• Evaluate genomic and transcriptional changes on baseline and resected tumor specimens.
 
• Evaluate changes in immune cell infiltration on baseline and resected tumor specimens. Changes in ctDNA.
 

### 8.1 Sample Size and Accrual Rate Considerations

#### 8.1.1 Sample Size and Power Estimate

27 evaluable patients will provide 87% power to detect a MPR rate of 50% as compared to a null rate of 22%, at the 5% significance level.

#### 8.1.2 Replacement Policy

All patients who receive a dose of osimertinib will be analyzed for safety and efficacy. Participants who discontinue from study participation prior to surgical resection may be replaced after discussion with the PI. Patients removed from study for unacceptable treatment related AE(s) will be followed until resolution or stabilization of all treatment related AEs to grade 2 or lower; however, they will not be replaced.

#### 8.1.3 Accrual estimates

This is a multi-institution study (UCSF and participating sites). Thoracic oncology sees approximately 300 new early stage lung adenocarcinoma patients per year with ~ 25% of these patients harboring EGFR-activating mutations. We predict that ~ 25 patients per year will be eligible for this study. UCSF and participating sites currently have no competing trials for this

patient population. We expect to fully accrue this study within 36 months of opening for patient enrollment.

## 8.2 Interim Analyses and Stopping Rules

An interim safety analysis will be performed following enrollment of 9 patients (33% of planned study population). A 97% disease control rate has been previously reported to osimertinib in the first-line setting in advanced EGFR-mutated NSCLC.[35] Even in the setting of standard of care resection, there is a high rate of pathologic upstaging relative to initial clinical staging. For example, among patients enrolled in CALGB9761 with clinical stage I NSCLC and PET scans negative for additional disease, 38.3% were subsequently upstaged on pathology.[52]

We would therefore consider conversion to unresectable status in two or more patients to reach threshold for early study discontinuation. In patients with evidence of clinical benefit (SD or PR) to osimertinib therapy on preoperative imaging, pathologic upstaging will not be considered an indication for study discontinuation unless it occurs at a rate greater than previously reported to standard of care (i.e., in 4 or more patients), as overall presence of disease response on imaging renders isolated occult lymph node progression unlikely.

Safety of the study will be continuously assessed by the PI and the DSMC. The study may be stopped early if there is deemed to be an unacceptable safety risk by either the PI or the DSMC.

## 8.3 Analyses Plans

### 8.3.1 Analysis Population

All patients who receive a dose of osimertinib will be analyzed for safety and efficacy. Participants who discontinue from study participation prior to surgical resection may be replaced after discussion with the Study PI.

Demographic and baseline characteristics will be summarized. In general, frequency distribution and percentage will be used to summarize categorical measurements, while mean with standard deviation and median with interquartile range will be used to describe symmetric and skewed continuous measurements, respectively. Univariate analysis among variables will be assessed using the two-sample t-test, Wilcoxon-rank-sum test, or Chi-square test, as appropriate.

### 8.3.2 Primary Analysis (or Analysis of Primary Endpoints)

MPR rate (primary endpoint) will be determined in patients who receive at least one dose of study drug.

Patients who receive one dose of study drug and become ineligible for surgery either because of disease progression or adverse event will be deemed not to have achieved MPR.

In patients who undergo surgical resection or their lung tumor resection specimens will be processed at the local institution following CAP and CLIA guidelines. Immediate sampling of the tumor and overnight fixation in 10% buffered formalin for paraffin embedding, usually within 20-24 hours after fixation. For histopathological evaluation, at least one sample per every 1-cm of diameter will be submitted for FFPE processing and pathology analysis. The local institutional study pathologist will assess each case for MPR, using percentage of viable tumor cells (cutoff as + MPR is  $\leq 10\%$  of viable tumor cells) as has been reported [24]. The pathological response should be reported as average percentage of viable tumor cells by slide examined.

Pathology slides (H&E and IHC and special stains) will be forwarded to the designated central pathologists for the study and MPR will be determined as described above.

In order to more fully evaluate the specimens associated with this trial, the central review pathologists will score the material using criteria as follows:

Pathological CR: Residual viable tumor: 0% MPR: Residual viable tumor:  $\leq 10\%$

Pathological response (not meeting major response criteria) 11-49% residual viable tumor. No pathological response: 50% or greater residual viable tumor.

Predominant reaction type: Necrosis, Fibrosis

**Tumors that exhibit  $\leq 10\%$  viable tumor will meet the criteria for an MPR as has been previously described [24].** The MPR rate will be reported with 95% confidence intervals.

As needed, a sub-set of tissues will be independently evaluated by both pathologists for assessment of inter-pathologist reproducibility for this scoring.

Whenever possible, the following will be included:

- Concurrent submission of pre-treatment biopsy or FNA sample. This can help inform pathologic evaluation in that pre-treatment necrosis can be assessed, within the context of potential sampling bias.
- Whenever feasible, all post-treatment surgical tumor samples will be submitted for pathologic examination (full lesion block-in), after tissue procurements have been completed.
- Samples will be identified, accrued and sent for central review in groups of no less than 10 cases to minimize criteria drift. If fewer than 10 cases are sent in any individual batch, the cases will be held until a minimum of 10 cases are available for review.

### 8.3.3 Secondary Analysis (or Analysis of Secondary Endpoints)

**5-Year DFS:** DFS will be calculated as 1+ the number of days from date of surgical resection to documented radiographic relapse/progression or death due to any cause over a period of 60 months. The Kaplan-Meier analysis will be used to calculate the median DFS with 95% confidence interval. 5-year DFS rate will be calculated as the percentage of patients who are disease free at 5 years. This will be calculated using the Kaplan-Meier method.

Assuming alpha of 0.05 and a set sample size of 27, as well as a null hypothesis of 50% 5-year DFS [53], we will have a power of 80% to detect a 25% increase in 5-year DFS.

**Objective Response Rate:** The objective response rate is defined as the best overall response recorded from the start of the treatment until time of surgery. The frequency and percentages of patients with a best ORR of CR, PR, SD, or PD will be determined. The objective response rate will be reported with 95% confidence intervals.

**Pathologic Complete Response Rate (pCR):** The pCR is defined as absence of (0%) viable tumor present histologically in the resected tumor specimen. Scoring for pathologic response is described above.

**5-Year Overall survival (OS) rate:** 5-year OS rate will be calculated using the Kaplan-Meier method. OS will be defined as the 1+ the number of days from surgical resection to death due to any cause over a period of 60 months. The Kaplan-Meier analysis will be used to calculate the median OS with 95% confidence interval.

**Depth of Response (DpR):** DpR will be defined as the percentage change in tumor burden by RECIST criteria at best response versus baseline imaging. DpR will be summarized using descriptive statistics and correlated with patient outcomes using hazard ratios via the Cox proportional hazards model.

**Safety and Tolerability:** AE terms recorded on the CRFs will be mapped to preferred terms using the MedDRA. Seriousness, severity grade and relationship to study treatment will be assessed by the investigator. Severity grade will be defined by the NCI CTCAE v4.03. Listings of AEs will be provided. Rate of conversion from operable to non-operative will be recorded as rate of patients initially assessed as surgically resectable, who are subsequently unable to undergo surgical resection due to either treatment-related AEs or PD. Rate of surgical complications occurring prior to the end of treatment visit will be recorded.

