### 3.5 Duration of Follow Up

Patients will be followed for safety assessments 30 days following the Day 15 post-operative visit, or removal from study, or until death, whichever occurs first. Patients removed from study for unacceptable treatment-related AE(s) will be followed until resolution or stabilization of all treatment related AEs to Grade 2 or lower. Patients whose disease is not resectable at the time of scheduled surgery will be managed per standard of care for patients with unresectable EGFR-mutant NSCLC. All patients will be followed for disease relapse and OS for up to 5 years.

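### OS is timed from surgical resection, so dosed patients who never have surgery drop out of the 5-year OS estimate, although the plan analyses all dosed patients for efficacy

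*Combined protocol and SAP*

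**What the plan says.** Three parts of the plan bear on OS.

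- **Time origin.** Section 8.3.3: "OS will be defined as the 1+ the number of days from surgical resection to death due to any cause", over 60 months, with Kaplan-Meier estimates of the 5-year rate and the median.
- **Population.** Section 8.3.1: "All patients who receive a dose of osimertinib will be analyzed for safety and efficacy". Section 8.1.2 says the same.
- **Follow-up.** Section 3.5: "All patients will be followed for disease relapse and OS for up to 5 years". The sentence just before it deals with patients who turn out not to be resectable.

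The plan expects some dosed patients to miss surgery. Section 3.5 provides for them: "Patients whose disease is not resectable at the time of scheduled surgery will be managed per standard of care". Section 8.2 sets a threshold at the look after 9 patients: "We would therefore consider conversion to unresectable status in two or more patients to reach threshold for early study discontinuation". Section 8.3.3 reports the rate of patients "who are subsequently unable to undergo surgical resection due to either treatment-related AEs or PD".

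Section 8.1.2 allows patients who discontinue before resection to be replaced. Patients removed for unacceptable treatment-related AEs are followed until "stabilization of all treatment related AEs to grade 2 or lower; however, they will not be replaced".

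For the primary endpoint the gap is closed. Section 8.3.2: "MPR rate (primary endpoint) will be determined in patients who receive at least one dose of study drug". It then counts dosed patients who become ineligible for surgery through progression or an AE as not having achieved MPR. OS has no matching rule.

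**The concern.** A Kaplan-Meier curve needs a day 0 for each patient. A dosed patient who dies before surgery, converts to unresectable, or leaves before surgery because of an AE or withdrawal has none under section 8.3.3. The stated population and the stated time origin cannot both be applied to that patient.

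If the origin is applied literally, these patients leave the curve, and a death on study drug before surgery is not an OS event. The trial gives drug before surgery and has unresectability as a study objective (section 2.2), so these are outcomes it set out to observe. If the origin is instead settled at analysis, it is chosen after outcomes are known in an open-label, single-arm study.

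The contact schedule does not resolve this. Sections 6.1.4 and 6.1.5 and Appendix 1 footnote 17 start the survival contacts at an end-of-treatment visit set by post-operative day 15 and run them to 5 years after surgery.

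**Working it through.** The plan states no sample size, power or assumed rate for OS, so there is no figure to reproduce. The contradiction follows from the text. The arithmetic below only gives its likely size.

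**Inputs**

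- From the documents: 27 patients (sections 3.2 and 8.1.1); at least one 28-day cycle and at most two; last dose 3 to 7 days before surgery; surgery within 14 days of the final scan (abstract, sections 3.1 and 3.4).
- Assumed, because the documents give no values: all-dosed 5-year OS *S* = 0.60 to 0.80; 5-year OS of unresected patients *u* = 0 to 0.40; number unresected *d* = 1 or 2; complete follow-up.

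**Step 1. Selection effect, shift of origin ignored**

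Not replaced (27 dosed, 27 − *d* resected):

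excess = (27*S* − *du*)/(27 − *d*) − *S* = *d*(*S* − *u*)/(27 − *d*)

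Replaced (27 resected, 27 + *d* dosed):

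excess = ((27 + *d*)*S* − *du*)/27 − *S* = *d*(*S* − *u*)/27

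The smallest value of *S* − *u* is 0.60 − 0.40 = 0.20 and the largest is 0.80 − 0 = 0.80.

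| Unresected | Not replaced | Replaced |
|---|---|---|
| *d* = 1 | 0.20/26 to 0.80/26 = 0.008 to 0.031 | 0.20/27 to 0.80/27 = 0.007 to 0.030 |
| *d* = 2 | 0.40/25 to 1.60/25 = 0.016 to 0.064 | 0.40/27 to 1.60/27 = 0.015 to 0.059 |

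This is about 1-3 points for one patient and 1-6 points for two. Replacement restores the number in the curve but hardly changes the excess, because the missing outcomes stay missing. The excess is zero if *u* = *S*.

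**Step 2. Effect of moving the origin to first dose**

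Earliest surgery is about day 28 + 3 = 31, and latest about day 56 + 14 = 70, ignoring visit windows and interruptions. At constant hazard, with 5 years = 1826.25 days, the gain is *S*^((1826.25 − *t*)/1826.25) − *S*. For *t* = 31 to 70:

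- *S* = 0.60: 0.005 to 0.012
- *S* = 0.70: 0.004 to 0.010
- *S* = 0.80: 0.003 to 0.007

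The earlier origin alone therefore raises 5-year OS by about 0.3-1.2 points.

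**Step 3. The two together**

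At the mildest corner (*S* = 0.60, *u* = 0.40, *d* = 1, not replaced), resected-only OS is (16.2 − 0.4)/26 = 0.608. All-dosed OS from first dose is 0.605 to 0.612. The net difference can have either sign there.

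**Step 4. Scale**

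With 19 of 27 alive (70%), the exact 95% confidence interval is 0.498 to 0.862, about 36 points wide.

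**The case against.** The strongest reply is that little depends on this. OS has no null, test, power or decision rule. Sections 2.3 and Table 8.1 also place long-term measures of efficacy under the exploratory objectives. The definition is explicit, so a reader can see that the curve starts at surgery, and 1-6 points is small beside a 36-point interval. These points limit the importance but do not remove the conflict. The abstract, section 2.4.2 and Table 8.1 all list 5-year OS as a secondary endpoint, and a confidence interval does not account for patients left out of the curve.

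Three further points stand and set limits.

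- **Progression.** A reader might infer that any patient who progresses before surgery is lost from OS. The documents do not support that. Section 3.4 makes progression a bar to cycle 2, not to surgery. A patient who progresses and is still resected has a start date.
- **Direction.** A reader might infer that the bias is always upward. That follows from assuming unresected survival of at most 40% and all-dosed survival of at least 60%. Neither range is in the documents, and Step 3 shows that the net difference can vanish or reverse.
- **Follow-up.** Patients who withdraw consent before surgery may contribute little survival data. They would be censored early under any definition, so the real shift could be smaller than shown.

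Resection is also a natural origin for the Cox model of DpR, since DpR is known by then. That matters for the fix, not for whether the gap exists.

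**Conclusion.** The point holds. Section 8.3.3 gives no OS start date to a dosed patient who never undergoes resection. Sections 8.1.2, 8.3.1 and 3.5 require that patient to be analysed for efficacy and followed for OS, and no other section fills the gap. Followed as written, 5-year OS describes patients who reached surgery.

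It will probably overstate OS for patients who start osimertinib, provided unresected patients survive less well. The size rests entirely on the assumed ranges and complete follow-up: about 1-3 points with one unresected patient and 1-6 with two, before the 0.3-1.2 point offset from the earlier origin.

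Three stronger readings are not supported. The primary result is not at risk, because section 8.3.2 already keeps progression and AE losses in the MPR denominator. Survival data on unresected patients are not unplanned, because section 3.5 follows everyone; only the anchor of their contacts is unclear. Timing DFS from resection is not an error. It needs a label, because it covers resected patients only while its power statement fixes the sample at 27.

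This should be corrected before OS is analysed. It concerns the clarity and interpretation of a secondary endpoint and does not threaten the trial's main conclusion.

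**What to change.** - **Section 8.3.3, OS.** Define OS from first dose of osimertinib to death from any cause in all dosed patients, censored at last contact. If wanted, keep OS from resection as a supplementary analysis labelled as resected patients only.
- **Section 6.1.5 and Appendix 1 footnote 17.** Anchor the survival contacts of patients without surgery to first dose, in line with the 5-year follow-up in section 3.5.
- **Section 8.3.3, DFS.** Keep resection as the origin, label it a resected-patient analysis, report its actual n, and compare it with the 50% null on that basis.
- **Optional.** Add a descriptive event-free survival from first dose in all dosed patients.

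**Cost.** An amendment to the wording and a defined contact schedule for the few patients without surgery. First-dose dates and survival status are already planned, and contacts to 5 years after surgery already cover 5 years from first dose in resected patients.

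**Downsides.** OS would include roughly 31 to 70 days of pre-surgical time, so it is slightly less comparable with surgery-based series. DpR is not known at first dose, so any Cox model of DpR against OS should start at the pre-surgical scan.

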### 2.4.2 Secondary Endpoints

- Radiographic decrease in maximum tumor diameter
- DpR
- 5-year DFS
- 5-year OS
- Complete pCR
- Treatment-emergent AEs, laboratory abnormalities and ECG abnormalities as determined by National Cancer Institute Common Toxicity Criteria (NCI-CTC) version 4.03 by investigator
- Rate of conversion to inoperable status due to treatment-related toxicity or PD
- Rate of surgical complications occurring prior to the end of treatment visit

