## 5.2 Dose Modifications and Dosing Delays

If a patient experiences a CTCAE grade 3 or higher and/or unacceptable toxicity including a DLT, not attributable to the disease or disease-related processes under investigation, dosing will be interrupted and supportive therapy administered as required in accordance with local practice/guidelines.

If a toxicity resolves or reverts to  $\leq$ CTCAE grade 2 within 3 weeks of onset, treatment with osimertinib may be restarted at the same dose (80 mg) or a lower dose (40 mg) using the rules below for dose modifications (Table 5.2) and with discussion and agreement with Principal Investigator (PI). There will be no individual modifications to dosing schedule in response to toxicity, only potential dose reduction or dose interruption.

On resolution of toxicity within 3 weeks: If an AE subsequently requires dose interruption, osimertinib may restart at the same dose or the reduced dose, on resolution/improvement of the AE at the discretion of the Investigator.

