**Table 5.3 Dose Modifications and Dosing Delays Tables for General Adverse Events**

Grade of Event	Management/Next Dose for Osimertinib
≤ Grade 1	No change in dose
Grade 2	Hold until ≤Grade 1 if clinically significant, otherwise no change in dose Resume at same dose level
Grade 3	Hold* until <Grade 2 Resume at one dose level lower, if indicated**
Grade 4	Off protocol therapy

\*Patients requiring a delay of >2 weeks should go off protocol therapy

\*\*Patients who do not tolerate 40 mg PO daily dose will be taken off protocol therapy

\*\*\*Alopecia/hair color changes are excluded from requirement for dose delays or modifications

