### 5.3 Monitoring and Toxicity Management

Each patient receiving osimertinib will be evaluable for safety. The safety parameters include all laboratory tests and hematological abnormalities, physical findings, ECG findings, echocardiography findings, and spontaneous reports of AEs reported to the investigator by patients.

Each patient will be assessed periodically for the development of any toxicity as outlined in Section 6 Study Procedures and Observations. Toxicity will be assessed according to the NCI CTCAE v4.03. Dose adjustments will be made according to the system showing the greatest degree of toxicity.

We will monitor for potential adverse effects including but not limited to fatigue, nausea, vomiting, dehydration, cytopenias, and signs and symptoms of infection. In addition we will monitor specifically for the following AEs of special interest (Please see the corresponding subsections in Section 6.2 for acute toxicity management and dose modifications).

- Rash/Dry Skin
- Diarrhea
- Ejection Fraction Changes
- Prolonged QTc
- Pneumonitis/ILD
- Liver Chemistry Elevations
- Hyperglycemia

Management of any grade 3 or higher toxicity should be discussed with the PI of the study.

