### **AEs based on examinations and tests**

Deterioration as compared to baseline in protocol-mandated laboratory values, vital signs, QTc, LVEF, and DLCO should only be reported as AEs if they fulfill any of the SAE criteria or are the reason for discontinuation of treatment with the IP.

If deterioration in a laboratory value/vital sign is associated with clinical signs and symptoms, the sign or symptom will be reported as an AE and the associated laboratory result/vital sign will be considered as additional information. Wherever possible, the reporting Investigator uses the clinical rather than the laboratory term (e.g., anemia versus low Hgb value). In the absence of clinical signs or symptoms, clinically relevant deteriorations in non-mandated parameters should be reported as AE(s).

Deterioration of a laboratory value, which is unequivocally due to PD, should not be reported as an AE/SAE.

Any new or aggravated clinically relevant abnormal medical finding at a physical examination as compared with the baseline assessment will be reported as an AE.

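### A symptom-free, non-serious LVEF fall that does not end treatment has no committed place in the safety reporting, and section 5.3.1 reads at odds with the MUGA/TTE schedule

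*Combined protocol and SAP*

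**What the plan says.** **Reporting rule.** Section 7.3.1, under AEs based on examinations and tests, covers deterioration from baseline in measurements that the protocol mandates. It says that vital signs, laboratory values, "QTc, LVEF, and DLCO should only be reported as AEs if they fulfill any of the SAE criteria or are the reason for discontinuation" of study drug. Where a changed laboratory value or vital sign comes with clinical signs or symptoms, the sign or symptom is reported.

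**Monitoring.** Section 5.3 counts among the safety parameters "ECG findings, echocardiography findings, and spontaneous reports of AEs reported to the investigator by patients". Its list of adverse events of special interest includes ejection fraction changes.

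**Endpoints.** Section 2.4.2 names "Treatment-emergent AEs, laboratory abnormalities and ECG abnormalities as determined by National Cancer Institute Common Toxicity Criteria". Table 8.1 has the matching entry, "Treatment-emergent AEs, laboratory abnormalities and ECG abnormalities as determined by NCI-CTC version 4.0 by investigator". Neither mentions LVEF or echocardiography.

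**Analysis.** For safety, section 8.3.3 commits to adverse-event listings ("Listings of AEs will be provided"), the rate of conversion to inoperable status and the rate of surgical complications. Sections 7.2 (Evaluation of Safety) and 8.4 add the population and the grading system. Section 8.3.1 gives general descriptive methods.

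**Measurement.** Section 5.3.1 has LVEF assessed at baseline and afterwards when the investigator suspects new cardiac impairment. Sections 6.1.2.3 and 6.1.2.6 and Appendix 1 schedule MUGA or TTE at Cycle 1 Day 28 (patients going to surgery after one cycle) and at Cycle 2 Day 28, with no such condition. At Cycle 2 Day 1 it is optional unless the patient has risk factors.

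**Stopping drug for LVEF.** Table 5.5 and section 5.3.1 require permanent discontinuation for symptomatic heart failure, or for symptom-free dysfunction lasting about four weeks.

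**The concern.** Safety is a secondary objective. Section 1.2.1 reports an association between osimertinib and heart failure or reduced LVEF, and exclusion criterion 14 admits patients with LVEF below 50% on a stable, optimised regimen. All are being prepared for lung surgery. The plan pays for an echo before surgery, but an investigator who follows the reporting rule leaves most symptom-free falls out of the adverse-event data, and nothing else commits the trial to summarising them. A published safety section could then be silent on LVEF although the values exist. A site that takes section 5.3.1 literally could omit the pre-surgery echo, and the values would not exist at all.

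**Working it through.** The plan states no figure for this point, so the main check is to follow one case through the text.

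**1. Trace a symptom-free, non-serious fall first seen at the last pre-surgery echo.**
- Serious-event exception: not met, by construction.
- Discontinuation exception: the LVEF rule needs about 4 weeks (28 days) of persistence. Section 3.4 puts surgery within 14 days of the final scan, with the last dose 3 to 7 days before surgery. If echo and scan fall on the same day, at most 14 − 3 = 11 dosing days remain. Section 6.1 allows ±3 days per visit procedure, so the echo could precede the scan by up to 6 days, giving at most 11 + 6 = 17 days. Both are below 28, so the persistence trigger is not reached on drug.
- Result: not an adverse event under 7.3.1, and so not in the listings.

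**2. Trace a fall found earlier.** A two-cycle patient with a fall on a Cycle 2 Day 1 echo has 28 − 1 = 27 days to Cycle 2 Day 28 and then up to 11 more dosing days, 38 in all. The trigger can be met, and the fall then becomes reportable. The same holds for a fall found early on clinical suspicion. The discontinuation route is therefore narrow but not closed.

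**3. Compare with the other special-interest items in section 5.3.**

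| Item | Route to an output |
|---|---|
| Rash/dry skin, diarrhea, pneumonitis/ILD | Clinical adverse events |
| QTc | Restricted by 7.3.1, but ECG abnormality is a named endpoint |
| Liver chemistry, glucose | Restricted by 7.3.1, but laboratory abnormality is a named endpoint |
| Ejection fraction | Restricted by 7.3.1; not a named endpoint |

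Ejection fraction is the one item whose symptom-free form has neither route.

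**4. What a table could show.** About 27 baseline/pre-surgery pairs are expected. Replacement under 8.1.2 could add some and early stopping could remove some, so 24 and 30 are used as assumed bounds.
- No falls, exact 95% upper limit = 1 − 0.025^(1/n): n = 24, 14.2%; n = 27, 12.8%; n = 30, 11.6%.
- One fall in 27: 1/27 = 3.7%, Clopper-Pearson 95% interval 0.1% to 19.0%.

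**5. Would there be anything to report?** The documents call the LVEF event rate low and give no number. For an assumed rate p, the chance of at least one case in 27 is 1 − (1 − p)^27:

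| Assumed p | Chance of ≥1 | Expected cases |
|---|---|---|
| 1% | 24% | 0.3 |
| 3% | 56% | 0.8 |
| 5% | 75% | 1.4 |
| 10% | 94% | 2.7 |

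**The case against.** The case against has real substance.

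- **The data are not lost.** Section 5.3 makes echo findings a safety parameter, section 9.6 puts study data on case report forms for safety monitoring and analysis, and section 8.3.1 supplies descriptive methods. The team could summarise LVEF unprompted. This stands: what is missing is a commitment, not the data.
- **The contrast with laboratory and ECG data is thin.** Section 8.3.3 promises no laboratory or ECG table either. This also stands. The difference lies in the endpoint lists, but those lists define what the trial undertakes to report.
- **Many important falls are captured.** Symptoms, serious events, events that end treatment, and treatment-related events that prevent surgery (8.3.3; Appendix 1, footnote 12) all have a route.
- **Section 5.3.1 is toxicity guidance** and can be read as adding a trigger to the schedule that section 6.1 sets. That reading is reasonable and probably intended, but the section does not say so.
- **The table would be imprecise and uncontrolled.** True, and it limits the value of the fix.

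Three stronger readings are tempting, and the documents do not support them.

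- A reader might infer from Table 5.3, where a grade 2 event leads to a hold "if clinically significant, otherwise no change in dose", that a mild fall can never become a reason for stopping. That table covers general events. Table 5.5 governs LVEF, sets no grade condition, and can be met by a fall found early enough.
- A reader might infer that the gap is confined to lower grades. The rule in 7.3.1 turns on seriousness and discontinuation, not grade.
- A reader might fault the absence of a post-surgery echo. The four-week rule governs osimertinib dosing, and section 3.4 gives no drug after surgery, so no dosing decision depends on one.

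**Conclusion.** The point holds as a gap in committed safety reporting and is worth a low-cost correction. Under the reporting rule as written, a symptom-free, non-serious LVEF fall that does not end treatment stays out of the adverse-event listings, and LVEF lacks the separate endpoint that covers the laboratory and ECG changes under the same rule. For a fall first seen at the last pre-surgery echo, the discontinuation route will seldom help, with about 11 dosing days left at most. That figure assumes echo and scan on the same day; allowing for visit windows does not change the conclusion.

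The wording of section 5.3.1 is a lesser, separate matter: read literally it conflicts with the schedule, and read generously it does not.

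The consequence is modest. It bears on completeness of a secondary safety objective, in about 27 patients and without a control group. The primary endpoint and the early-discontinuation rule in section 8.2 are unaffected.

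**What to change.** 1. In section 2.4.2 and Table 8.1, add LVEF to the safety endpoint beside laboratory and ECG abnormalities.
2. In section 8.3.3, add one descriptive summary in dosed patients, using the methods of 8.3.1: change from baseline to the last pre-surgery value; number and percentage by CTCAE v4.03 grade, whether or not recorded as an adverse event; and the number of dosed patients with no second value.
3. In section 5.3.1, state that LVEF tests prompted by clinical suspicion are additional to the MUGA/TTE scheduled in 6.1.2 and Appendix 1.

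The cost is one phrase in two places, one table of values already scheduled, and one clarifying sentence. No new procedure is needed if the Appendix 1 schedule applies. The downside is a low-precision, uncontrolled table, which should be presented as descriptive only. Section 6.1.1.1 ties cardiac assessment to the TAGRISSO core data sheet, which is not among the documents, so the new sentence should be checked against it.
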